5.4.4. Contraception Rules

Refer to Section 5.2 (inclusion criteria).

6. INVESTIGATIONAL MEDICINAL PRODUCT

6.1. Study Agent

6.1.1. Physico-chemical characteristics

Active substance: CPL500036

Chemical name: 7-5,8-dimethyl-[1,2,4]triazolo[1,5-a]pyrazin-2-yl}-2-

phenylimidazo[1,2-a]pyrimidine

Chemical structure:

Molecular formula: C19H15N7

Molecular weight: 341,37 g/mol

6.1.2. Formulation

[figure not shown]

Table 6	6 The composition of powder filled into gelatin capsule.		
6.2.	Identity of the Investigational Medicinal Products		
6.3.	Supply, Packaging, Labelling and Storage		

6.4. Subject Identification and Randomization

6.4.1. Screening Numbers

At Screening, subjects will be assigned a unique subject identification number (or subject identifier). Enrolled subjects who drop out of the clinical study before randomization will retain their subject identification number.

6.4.2. Randomization Numbers

Prior to dosing, on Day 0, subjects will be assigned a randomization number in accordance with the randomization code generated by eCRF platform. Randomization procedure is to be performed to minimize bias in the assignment of subjects to treatment groups. Subjects are to be randomized in 1:1:1 ratio (a stratified block is to be implemented: geographical location, PK group, PANSS baseline score).

Once a randomization number has been allocated to one subject, it may not be assigned to another subject.

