5.2. Inclusion Criteria

Patients eligible for inclusion in this study have to fulfil all of the following criteria:

- 1. The patient has a primary diagnosis of schizophrenia (Diagnostic and Statistical Manual of Mental Disorders, 5th Edition [DSM-5], 295.90) confirmed by clinical interview (Structured Clinical Interview for DSM-5 Clinical Trial Version [SCID-5-CT]). The participant's initial diagnosis must be greater than or equal to (≥) 2 year before Screening.
- 2. Male or female patient aged 18 to 65, inclusive, at Screening.
- 3. The patient's psychotic symptoms were exacerbated within 2 months (60 days) prior to Screening (e.g., aggravated delusion).
- 4. The patient has a score of 5 (moderate severe) or higher in 3 or more items of the following PANSS items at Screening and Day -1: delusions (P1), conceptual disorganization (P2), hallucinations (P3), suspiciousness (P6), and unusual thought content (G9).
- 5. The patient has a PANSS Total Score of 80 or higher during Screening and on Day -1.
- 6. A female is eligible to participate if she is not pregnant (negative pregnancy test at Screening and Day -1), not breastfeeding, and at least 1 of the following conditions applies:
 - a) Not a woman of childbearing potential (a woman is considered to be of non-childbearing potential if she is post-menopausal for at least 12 months or is surgically sterile [hysterectomy, bilateral oophorectomy, tubal ligation]).

- b) Woman of childbearing potential, who agree to use contraceptive methods during the Treatment Period and for at least 28 days after the last dose of the study drug. The following are acceptable contraceptive methods: bilateral tubal occlusion, male sterilization, established proper use of hormonal contraceptives that inhibit ovulation, hormone-releasing intrauterine devices and copper intrauterine devices, male or female condom with spermicide; and cap, diaphragm, or sponge with spermicide.
- 7. Male patients must agree to use a barrier method of contraceptive (condom + spermicide gel) for at least 90 days after the last dose of the study drug.
- 8. The patient has a Clinical Global Impression Scale- Severity of Illness Scale (CGI-S) of 4 or greater at Screening and Day -1.
- 9. The patient is able to and agrees to remain off prior antipsychotic medication and all excluded medications as outlined in the protocol for the duration of the Treatment Period.

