8.5.1. Positive and Negative Syndrome Scale

The PANSS is a 30-item scale used to measure symptoms of schizophrenia. The scale has 7 positive symptom items, 7 negative symptom items, and 16 general psychopathology symptom items. Each item is scored on a 7-point scale by the clinical rater based on a clinical interview with the patient.

Positive and Negative Syndrome Scale will be performed at the time points detailed in the Schedule of Assessments (Table 1) and as detailed below:

The efficacy assessment (PANSS) will be performed once at Screening (Day -10 to -2); once at Baseline (Day -1); on Days 1, 7, 14, 21 and 28 when start of ratings is to be within 5 minutes before or after 2h post-dose (it will be performed before any other scale).

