ATC	Anatomical Therapeutic Chemical classification
AUC	area under the curve
BACS	Brief Assessment of Cognition in Schizophrenia
AUC _(0-inf)	Area under plasma concentration-time curve from time zero extrapolated to infinity
AUC _(0-tau)	Area under plasma concentration-time in the dosing interval, i.e. from time zero to exactly 24 hours
AUC _(0-24h)	Area under plasma concentration-time curve from time zero to 24 hours measured or extrapolated to the actual sampling time (referred as AUC ₀₋₂₄ in Clinical Study Protocol)
ВМІ	Body Mass Index
CGI-I	Clinical Global Impression Scale – Improvement
CGI-S	Clinical Global Impression – Severity
CL/F	apparent clearance
C _{max}	maximum observed concentration
Ctrough	Observed trough concentrations
CONSORT	Consolidated Standards of Reporting Trials
CSR	Clinical Study Report
C-SSRS	Columbia Suicide Severity Rating Scale
D	dose
ECG	electrocardiogram
(e)CRF	(electronic) Case Report Form
ESRS	Extrapyramidal Symptom Rating Scale
F	Bioavailability
FAS	Full Analysis Set
ICH	International Council for Harmonisation of Technical Requirements for Pharmaceuticals for Human Use
IMP	Investigational Medicinal Product
IWRS	Interactive Web Response System
Kel	elimination rate constant

MedDRA	Medical Dictionary for Regulatory Activities			
NA	not available			
PANSS	Positive and Negative Syndrome Scale			
PD	pharmacodynamic			
PK	pharmacokinetic			
PP	per protocol population			
PS	Pharmacokinetic Set			
PSPC	Pharmacokinetic Set for parameter calculation			
PT	preferred term			
SAE	serious adverse event			
SS	safety set population			
SD	standard deviation			
SOC	System Organ Class			
SOP	Standard Operating Procedure			
t _{1/2}	half-life			
t _{max}	Time corresponding to occurrence of C_{max} , i.e. the time after administration of a drug when the C_{max} is reached			
TEAE	treatment emergent adverse event			
TESAE	treatment emergent serious adverse event			
V _z /F	apparent volume of distribution during terminal phase			
WHO	World Health Organization			

1. Introduction

This statistical analysis plan reflects study protocol 02PDE2019 version 4.0, dated 16-May-2024. It follows the principles of the Guidelines ICH E3 and ICH E9.

All aspects of the statistical analysis shall be covered by this document. It provides a technical and detailed description of handling the collected data and statistical methods deployed.

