2.3.2. Randomization and blinding

Both subjects and investigators will be blinded to treatment assignment using IWRS system. A computer-generated randomization schedule prepared by prior to study initiation will be used. The randomization will be balanced by using randomly permuted blocks of variable length and will be stratified by PANSS score at Baseline (Day -1) (with two categories: low <95, high ≥95). Investigator will be able to break the blind for a given subject, in case of emergency, using tool provided within eCRF.

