3.4. Changes from specifications in the protocol

Not applicable.

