4.1.1.7. Positive and Negative Syndrome Scale (PANSS)

The PANSS is a 30-item scale used to measure symptoms of schizophrenia. The scale has 7 positive symptom items, 7 negative symptom items, and 16 general psychopathology symptom items. Each item is scored on a 7-point scale by the clinical rater based on a clinical interview with the patient. The efficacy assessment (PANSS) will be performed once at Screening; Baseline; on Days 1, 7, 14, 21 (before any other scale). Results of PANSS are calculated directly in the eCRF according to the formulas:

- Positive score: P1 + P2 + P3 + P4 + P5 + P6 + P7
- Negative score: N1 + N2 + N3 + N4 + N5 + N6 + N7
- Composite score: Positive score Negative score
- General: G1 + G2 + G3 + G4 + G5 + G6 + G7 + G8 + G9 + G10 + G11 + G12 + G13
 + G14 + G15 + G16
- Anergia: N1 + N2 + G7 + G10
- Thought Disturbance: P2 + P3 + P5 + G9
- Activation: P4 + G4 + G5
- Paranoid/Belligerence: P6 + P7 + G8
- Depression: G1 + G2 + G3 + G6
- Supplemental: P4 + P7 + G6 + S1 + S2 + S3
- Total score: Positive score + Negative score + General score

Where P = POSITIVE, N = NEGATIVE, G = GENERAL, S = SUPPLEMENTAL subsection of PANSS questionnaire.

Disease activity will be measured by PANSS Total Score and classified as low (PANSS <95) and high (PANSS >= 95).

Assessment of clinical responder will be performed based on the PANSS Total Score and is defined as a >= 30% decrease from baseline and calculated from the formula:

PANSS decrease = (PANSS at week X - PANSS at baseline)/(PANSS at baseline -30) * (-100%).

The adjustment of -30 points is due to the fact that PANSS total score ranges from 30 to 210 points. When unadjusted scores are used to calculate percentage change from baseline, it results in lower values of the percentage change, thus underestimating the response to the treatment and decreasing the proportion of responders (Leucht et al 2010).

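### Protocol and SAP list different randomisation strata, and the primary MMRM has no term for baseline PANSS, the one factor common to both lists; the cost is a little power and the error is conservative

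*Protocol*

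**What the plan says.** **Strata.** Protocol 6.4.2 lists three: "a stratified block is to be implemented: geographical location, PK group, PANSS baseline score". It gives no cut-point and does not say which PANSS score is meant. SAP 2.3.2 says the randomisation "will be stratified by PANSS score at Baseline (Day -1) (with two categories: low <95, high ≥95" and mentions neither geography nor PK group. The SAP opens with "This statistical analysis plan reflects study protocol 02PDE2019 version 4.0", and its Section 3.4, on changes from the protocol, reads "Not applicable". SAP 4.1.1.7 ties the cut to the Total score: "Disease activity will be measured by PANSS Total Score and classified as low (PANSS <95".

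**Primary model.** Protocol 10.3 and the R formula in SAP 4.7.1 contain treatment, timepoint, treatment-by-timepoint, site and a baseline score. Neither has a term for the PANSS stratum or for PK group. SAP 4.7.2 carries the same approach to the continuous secondary endpoints. Its logistic model for the binary endpoints does name baseline PANSS Total as a covariate.

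**Synopsis.** The current statistical methods text in Protocol 1.1 gives the interaction as site-by-timepoint and has no treatment-by-timepoint term.

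**The concern.** When randomisation is stratified on a prognostic factor, the arms are balanced on it, so the treatment difference varies less than it would under simple randomisation. A model without the factor does not see that. It leaves the factor's variance in the residual and reports too large a standard error. The trial then carries the complexity of stratifying and gives up part of the benefit. Stated power is only 80%, at a 10% two-sided level.

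The two lists also leave a reader unable to tell which factors were used, and so whether PK group belongs in the model as well.

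**Working it through.** **1. The plan's own figure.** Inputs from Protocol 10.16: 50 per group, effect size 0.5, two-sample t-test, two-sided 10%. Noncentrality = 0.5 × √(50/2) = 2.5; critical value t(0.95, 98 df) = 1.661; power = 0.799. The stated 80% reproduces. With one degree of freedom fewer, power is still 0.799.

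**2. Can the baseline covariate stand in for the stratum?** On the subscales, the protocol says "The scale has 7 positive symptom items, 7 negative symptom items", each item scored on a 7-point scale. The positive subscale therefore cannot exceed 7 × 7 = 49, and a cut at 95 cannot refer to it. The SAP says "PANSS total score ranges from 30 to 210 points". The entry rule is "The patient has a PANSS Total Score of 80 or higher during Screening and on Day -1", so the strata are 80 to 94 and 95 or more. For a 50:50 split of a normal score, the share of the stratum's variance explained by the positive baseline is about ρ² × 2/π, where ρ is the Total–positive correlation. With ρ assumed between 0.4 and 0.8, that is 0.16 × 0.637 = 10% to 0.64 × 0.637 = 41%. It is a partial proxy.

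**3. Size of the effect at Week 4.** Let r be the partial correlation of the stratum with Week 4 change, given site and positive baseline, and k = √(1 − r²). The documents give no value for r; 0.1 to 0.3 is assumed.

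- Standard error overstated by the factor 1/k.
- True size without the stratum = 2 × [1 − F(1.661/k)], with F the t distribution on 98 df.
- Power from the noncentral t with noncentrality 2.5/k: critical value 1.661/k without the stratum, and the usual critical value with it.

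| r | SE overstated | True size | Power without | Power with | Loss (points) |
|---|---|---|---|---|---|
| 0.1 | 0.5% | 9.8% | 0.800 | 0.802 | 0.2 |
| 0.2 | 2.1% | 9.3% | 0.804 | 0.813 | 0.9 |
| 0.3 | 4.8% | 8.5% | 0.810 | 0.831 | 2.1 |

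**4. Simulation.** 20,000 three-arm trials per r were analysed by Week 4 ANCOVA with site and positive baseline in the model. Assumptions: 150 completers, permuted blocks of 3 and 6 within PANSS stratum, 50:50 strata, 10 sites, Total–positive correlation 0.6. Without the stratum the SE was overstated by 0.4, 2.0 and 4.8%, and size was 0.099, 0.096 and 0.089 for r = 0.1, 0.2 and 0.3. Power without and with the stratum was 0.772/0.773, 0.780/0.789 and 0.786/0.810. At r = 0 the term cost 0.1 point (0.775/0.774). For a PANSS Total outcome with continuous baseline Total already in the model, the dichotomy gained nothing (0.774/0.772).

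**5. Which term to add.** Steps 3 and 4 concern a single visit, where the stratum has its own Week 4 coefficient. The MMRM uses five visits, including Day 1. A main effect alone fits one coefficient c to all of them. Suppose the stratum effect rises linearly from 0 on Day 1 to g at Week 4, with g = r/k in residual SD units. The Week 4 SE is then overstated by √(1 + (g − c)²). Take r = 0.3, so g = 0.3/0.954 = 0.3145.

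- No term: √(1 + 0.0989) = 1.048.
- Main effect, equal visit SDs: c = 0.5g, so √(1 + 0.157²) = 1.012. This recovers (4.8 − 1.2)/4.8 = 75% of the gain.
- Main effect, visit SDs rising linearly from 0.3 to 1.0, compound-symmetry correlation 0.8: generalised least squares gives c = −0.28g, so √(1 + 0.4026²) = 1.078. This is worse than leaving the stratum out.

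A stratum-by-timepoint term restores the Week 4 coefficient and with it the gains in step 3. It adds 1 + 4 = 5 degrees of freedom for two strata and five visits.

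**The case against.** The best case for leaving the model alone is that the stake is slight and rests on an unsourced correlation. At r = 0 nothing is gained. At r = 0.1 the gain is 0.1 to 0.2 points, and the simulated size of 0.099 is within Monte Carlo error (about 0.002) of 0.100. The positive baseline already carries part of the stratum, site covers geography indirectly, and the PANSS categories are examined as subgroups (SAP 3.2 and 4.7.3). All of this stands, and it limits the point to an inexpensive improvement. A subgroup analysis does not, however, correct the standard error of the overall comparison.

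The objection to a simple main effect also stands: by step 5 it could lose precision.

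Three stronger readings are tempting, and the documents support none of them.

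- *The omission inflates type I error or biases the estimate.* It does neither; the test is conservative.
- *The SAP shows that the randomisation scheme was changed.* SAP 2.3.2 sits in the overview of the protocol and may simply be an incomplete summary.
- *The synopsis leaves the trial without a Week 4 contrast.* Taken alone, its model would give one treatment effect shared by all visits. Section 10.3 and the SAP formula are the operative specifications, both contain treatment-by-timepoint, and SAP 4.7.1 promises comparisons at each timepoint. The conflict is confined to the synopsis.

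**Conclusion.** The point holds as a modest one. The lists of strata differ without acknowledgement, and baseline PANSS, common to both, has no term for its stratum in the primary MMRM or in the continuous secondary models that follow it. The figures in step 3 are the whole of the statistical cost, all in the conservative direction. They depend on r between 0.1 and 0.3, and the choice of term depends on an assumed time course and visit variances; none of these is in the documents. The mismatched lists and the synopsis interaction are matters of wording and do not alter the operative analysis.

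**What to change.** **(a) Model.** Add the PANSS Total stratum with its timepoint interaction, for example `CHANGE ~ TREATMENT * TIMEPOINT + SITE + BASELINE + PANSS_STRATUM * TIMEPOINT + us(VISIT|ID)`. Do the same in the continuous secondary models whose own baseline is not PANSS Total: negative, general psychopathology, Marder factors, CGI-S and BACS. Leave the PANSS Total model as it is. Add PK group in the same way only if it was actually a stratum. Omit the PANSS term within the PANSS subgroups, where it is constant. The variables are already collected and the five degrees of freedom are negligible. If unblinding has already taken place, keep the planned model as primary and report this one as a labelled sensitivity analysis.

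**(b) Strata wording.** State the strata actually used, with the cut and the score it applies to, identically in Protocol 6.4.2 and SAP 2.3.2. Record any difference from the protocol in SAP 3.4.

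**(c) Synopsis wording.** In Protocol 1.1, replace the site-by-timepoint interaction with treatment-by-timepoint, to match Section 10.3 and the SAP formula.

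Items (b) and (c) cost only the edits.

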6.5. Administration of Investigational Medicinal Products

Starting from Day 1, the IMP will be administered after a minimum 10-hours overnight fast with approximately 240 mL water. Subjects must remain in an upright position for at least 2 hours after dosing. The IMP is to be administered approximately at the same time each day.

Fasting requirement after IMP intake are described in Section 5.4.1.

For dosing details, see Section 6.6 below.

6.6. Dosing

To maintain double-blind manner, every patient will take the same number of capsules. Depending on the dose (20 mg or 40 mg) and the type of product (PG20 or placebo) intended for patient, he/she will take:

- 4 capsules of PG20: 40 mg,
- 2 capsules of PG20 and 2 capsules of placebo: 20 mg,
- 4 capsules of placebo.

In this way, both the patient and the Investigator will not know which product is administered to the patient.

6.7. Compliance, IMP accountability

Dosing will be performed by trained, qualified personnel designated by the Investigator. A hand and mouth check will be performed after dosing to ensure the subjects have swallowed the dose administered. The date and time of dosing will be documented on each dosing day. Comments will be recorded if there are any deviations from the planned dosing procedures. A single dose is to be considered as a compliant when all 4 capsules are administered and administration is without any emesis occurring within 2h after IMP administration. A patient is to be considered as compliant with dosing regimen when at least 80 % of the doses are compliant (at least 22 doses).

The Sponsor shall supply an adequate quantity of the investigational medicinal product (IMP) and the placebo, both for administration and as a backup, along with the respective certificates of analysis (CoA). Appropriate sealing of packages with the IMP/placebo and adequacy of the information included on the package labels is to be examined by the designated unblinded study person (pharmacist) in the clinical centre. The amount of each product is to be sufficient to account for any loss resulting from its potential damage or subject's withdrawal. The unblinded persons are obliged to store the products in a safe place, with limited access to third parties. The products are to be securely stored under pre-specified conditions, in accordance with applicable regulatory requirements. The products are to remain under the supervision of the designated study person and are to be released solely for the administration purposes, according to the study protocol. The study designated person is to be responsible for the investigational product during the whole study period. At the end of the study, a number of unused IMP is to be determined, and the product is to be returned to the Sponsor along with used containers. Adequate records documenting receipt, use or other disposition of the investigational product is to be kept by the designated person. The unblinded study monitor is to verify these documents throughout the course of the study.

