• the subject suffers from severe emesis within 4 hours after two consecutive days of drug administration. If emesis occurs within 4 hours post-dose and is to be mild or moderate or emesis occurs after 4 hours post-dose, discontinuation of the subject depends on Investigator's judgement and decision.

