3.1. Analysis populations

The following populations are to be analyzed:

- Full Analysis Set (FAS): All patients randomized to either CPL500036 or placebo based on planned treatment regimen irrespective of their compliance to the planned course of treatment (intent-to-treat principle).
- Per Protocol (PP) Set: Patients from the FAS who completed the Treatment Period (Day 28) on study treatment without a major protocol deviation. Protocol deviations will be determined prior to unblinding.
- Safety Analysis Set (SS): All patients who received at least 1 dose of study treatment (either CPL500036 or placebo).
- Pharmacokinetic Set (PS): All patients in the safety set with at least 1 evaluable PK parameter.
- Pharmacokinetic Set for parameter calculation (PSPC): All patients in the safety set with extensive PK sampling that have at least 1 PK parameter evaluable and without any major protocol deviation thought to interfere with the absorption, distribution, metabolism, and excretion of CPL500036.

The FAS will be the primary analysis set used for all efficacy analyses and the PP analysis set will be used for supportive analyses of the primary and secondary efficacy endpoints. Patients will be included in the treatment group they were randomized to. The SS will be used for all safety analyses and patients will be included in the treatment group based on the treatment they actually received.

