4.1.1.6. Drug adherence

A subject is considered as a complier with dosing regimen when at least 80% (that is 23 out of 28 planned doses) of the IMP are compliant - meaning that patient took a full dose consisting of four capsules.

Drug adherence is defined as a number of capsules consumed divided by 112 (4 capsules per day in 28 days) or 4 multiplied by the number of days subject is in the study during the active period (if early terminated).

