4.1.1.14. Pharmacokinetic parameters

PK parameters to be estimated according to the protocol:

- AUC_(0-24h): The area under the curve of plasma concentration vs time, from time point zero up to the time 24h after administration, unit: [ng*h/mL]. AUC_(0-24h) will be calculated according to the linear trapezoidal rule using actual sampling times and extrapolated basing on Kel if concentration at 24 h is below LLOQ.
- C_{max}: Maximum plasma concentration, unit: [ng/mL]. C_{max} defines the maximum concentration of the drug substance in plasma during dosing period. C_{max} will be obtained directly from the measured concentrations.
- AUC_(0-inf): The area under the curve of plasma concentration vs time, from time point zero extrapolated to infinity, unit: [ng*h/mL]. AUC_(0-inf) = AUC_(0-t) + C_t /K_{el}, C_t is the last measurable analyte concentration in plasma and K_{el} is the terminal elimination rate constant.
- t_{max}: Time to reach maximum plasma concentration, unit: [h]. The t_{max} will be obtained directly from the actual sampling times.
- K_{el}: Terminal elimination rate constant, unit: [1/h]. K_{el} will be estimated via linear regression of time versus log of concentration. This parameter will be calculated by linear least squares regression analysis using at least last three non-zero plasma concentration values. C_{max} values will not be included in K_{el} calculation. K_{el} will only be calculated if the adjusted coefficient of determination of exponential fit (R² adjusted) is not less than 0.7 (R² ≥ 0.7).
- t_{1/2}: Plasma elimination half-life, unit: [h]. The t_{1/2} will be calculated as 0.693/K_{el}.
- CL/F: apparent systemic clearance, calculated as dose administered in dosing interval divided by AUC_(0-inf) on Day 1 or divided by AUC_(0-tau).
- Vz/F: apparent volume of distribution; a hypothetical volume of fluid into which the drug is dispersed. It is calculated as Dose/(K_{el}*AUC_(0-inf)) for Day 1 and Dose/(K_{el}*AUC_(0-tau)) for Day 7.
- C_{trough}: the trough concentration is the concentration reached by the drug immediately before the next dose is administered as well as 24 h after the last dose administration.

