Additional plasma concentration/time box plots with individual points will be presented for extensive sampling (Days 1 to 7 and Day 28) and sparse sampling (Days 1, 7, and 28) for:

- pre-dose,
- 2 h after administration.

Missing drug concentration data (no value) will be omitted from PK calculations. Drug concentration data below LLOQ will be treated in pharmacokinetic analysis as follows:

- 1. If the concentration below LLOQ is recorded after the last measurable concentration in the dosing interval, then it is omitted from calculations.
- 2. In other cases the concentration below LLOQ concentration value is set to zero.
- 3. If an entire concentration-time profile below LLOQ, the profile will be excluded from the PK analysis.
- 4. A profile of patient with very low concentrations will be excluded from the PK analysis. A profile is considered to have very low concentrations if the $AUC_{(0-24h)}$ for that day is less than 5% of the geometric mean $AUC_{(0-24h)}$, which should be calculated without inclusion of data from the patient.

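### The protocol's 2 h emesis criterion is not carried into the SAP's compliance definition or PK profile exclusions, so a partly lost Day 1 or Day 7 dose can stay in the PK summaries and bias exposure and clearance (minor)

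*Protocol*

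**What the plan says.** Protocol 6.7 defines a compliant single dose by two conditions: all four capsules are administered, and "administration is without any emesis occurring within 2h after IMP administration". SAP 4.1.1.6 keeps only the first, "meaning that patient took a full dose consisting of four capsules", while SAP 3.4 records no changes from the protocol.

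Protocol 7.1.1.1 expects early vomiting in patients who continue. Withdrawal is mandatory for severe emesis soon after dosing on two days running. "If emesis occurs within 4 hours post-dose and is to be mild or moderate", continuation is left to the Investigator's judgement.

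SAP 4.6 has two rules that remove a whole profile, both based on concentration:

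- "If an entire concentration-time profile below LLOQ, the profile will be excluded from the PK analysis".
- "A profile of patient with very low concentrations will be excluded from the PK analysis", where very low means that AUC(0-24h) "for that day is less than 5% of the geometric mean" calculated without that patient.

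SAP 3.1 defines two PK sets, and SAP 4.6 analyses both. PS needs only one evaluable parameter. PSPC is limited to extensively sampled patients "without any major protocol deviation thought to interfere with the absorption" or other disposition of the drug. SAP 4.1.1.14 defines CL/F as "apparent systemic clearance, calculated as dose administered in dosing interval divided by" AUC, and Vz/F likewise has the dose in the numerator.

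**The concern.** The protocol treats a dose followed by emesis within 2 h as not properly taken. No PK passage in the SAP uses that information. If part of the dose is lost on a PK day, AUC and Cmax fall, but the numerator of CL/F and Vz/F remains the administered dose, so both parameters rise. The profile is kept unless exposure is almost nil.

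The PK profile is a stated secondary objective. The extensive subset has about 17 patients per dose, few enough for one distorted profile to be visible in a mean. The additional analyses in SAP 4.10 (Day 7/Day 1 accumulation, dose-normalised linearity, intra-subject variability in AUC) would inherit the error. For PS there is also no rule fixed in advance, so whether to keep such a profile could become a matter of choice after the results are known.

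**Working it through.** **Inputs.** 55 patients randomised per group (protocol 10.16). About 30%, or 17 per group, have extensive PK sampling (protocol 4.1). The 5% cut-off is in SAP 4.6 and the parameter formulas are in SAP 4.1.1.14. Three quantities are not in the documents and are assumed: the fraction f of usual exposure that remains, the emesis rate, and the half-life.

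**The plan's own figure.** 0.30 × 55 = 16.5, rounded up to 17. This reproduces. The sparse group is 55 − 17 = 38 per dose.

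**Effect on the individual profile, Day 1.** With Kel unchanged, AUC is multiplied by f. CL/F = Dose/AUC and Vz/F = Dose/(Kel × AUC) are therefore multiplied by 1/f. The 5% rule keeps any profile with f of 0.05 or more (taking the other patients' geometric mean as usual exposure), so an individual CL/F up to 1/0.05 = 20 times too high can be retained.

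**Effect on the group summary, Day 1, one affected profile of 17** (other patients alike, between-patient variation ignored):

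- geometric mean AUC ratio = f^(1/17)
- geometric mean CL/F ratio = f^(−1/17)
- arithmetic mean CL/F ratio = (16 + 1/f)/17

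| f | Geometric mean AUC | Geometric mean CL/F | Arithmetic mean CL/F |
|---|---|---|---|
| 0.5 | 0.960 (−4%) | +4% | 18/17 = 1.059 (+6%) |
| 0.3 | 0.932 (−7%) | +7% | 19.33/17 = 1.137 (+14%) |
| 0.1 | 0.873 (−13%) | +14.5% | 26/17 = 1.529 (+53%) |
| 0.9 | −0.6% | +0.6% | +0.7% |

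None of these profiles is removed by the 5% rule. The last row shows that emesis after most of the drug has been absorbed hardly matters.

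**Sparse patients.** With one affected profile of 38, the geometric mean AUC ratio is 0.5^(1/38) = 0.982 to 0.1^(1/38) = 0.941, or about −2% to −6%. This supposes that AUC(0-24h) can be obtained for all 38, although sparse sampling stops at 8 h.

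**Day 7.** Under an assumed linear one-compartment model, earlier doses contribute a share c = exp(−24 × ln2/t½) of the Day 7 AUC. The retained fraction is then c + f(1 − c), which is larger than f. At t½ = 8 h, c = 0.125, and f = 0.5 retains 0.5625, so CL/F is 1/0.5625 = 1.78 times too high rather than 2 times. The same carry-over also makes the 5% rule less able to act. Once t½ exceeds 24 × ln2/ln20 = 5.6 h, even complete loss of the Day 7 dose leaves more than 5% of AUC.

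**The case against.** The strongest reply is that the two-set design already deals with this. Protocol 6.7 asks for comments on deviations from planned dosing and then classes a dose with early emesis as non-compliant. A vomited dose could therefore be judged a major deviation affecting absorption, and the patient removed from PSPC. SAP 3.3 and 4.2 place the classification of deviations at a blinded review with minutes finalised before unblinding, and exclusions from the PK populations are listed with reasons. Comparing PS with PSPC would then show the effect.

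Much of this stands. A reader might infer that vomiting is only an adverse event and so can never lead to exclusion from PSPC, or that the 5% rule is the only way out. The documents say neither. Emesis is absent from SAP Table 2, but that table lists reasons for exclusion from PP, and SAP 3.3 allows a data review plan to add criteria. Nor would every exclusion be a choice made after unblinding.

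The PSPC route is nevertheless incomplete. It is discretionary, does not name emesis, removes the patient rather than the affected day, and does not reach the sparse-sampled patients (about 70%), whose only PK set is PS.

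The size is also open to challenge, with reason. The common drug-related Phase I events listed in protocol 2.5 do not include vomiting. The +53% applies to an arithmetic mean at f = 0.1; SAP 4.6 also reports the geometric mean and median, and the median would barely move.

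**Conclusion.** The point holds as a minor one. The protocol's emesis criterion is lost between the two documents, and following the SAP as written keeps a partly lost Day 1 or Day 7 dose in PS. The direction of the bias (lower AUC and Cmax, higher CL/F and Vz/F) follows from the SAP's formulas whenever drug is lost.

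The size is conditional. It rests on one affected profile, an assumed f between 0.1 and 0.5, unchanged Kel, and Day 1 data. On that basis geometric means shift by roughly 4% to 15% among 17 extensive patients, and geometric mean AUC by about 2% to 6% among 38 sparse ones. The arithmetic mean of CL/F is more sensitive. Day 7 losses are smaller because of carry-over, by an amount that depends on the half-life.

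A reader might conclude that the PK results will be seriously distorted. The documents do not support that: they give no emesis rate, and late emesis has little effect. PK here is secondary and descriptive, and the efficacy conclusion is untouched.

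**What to change.** Add a rule to SAP 4.6. When emesis is documented within the protocol's 2 h window after the Day 1 or Day 7 dose, that day's exposure-dependent parameters (AUC, Cmax, tmax, CL/F, Vz/F, and the Day 7/Day 1 and dose-normalised ratios built on them) are listed and flagged but left out of the main PS and PSPC summaries. Give a summary of all profiles as a check. Half-life may be kept where the Kel criteria are met, because it does not depend on the amount absorbed under the model used here.

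Decide profile by profile at the blinded data review already planned, from emesis and dosing times alone, so that no concentrations need to be seen.

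Two supporting changes are needed:

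- Record the emesis onset time on PK days and state how an unknown time is handled. Protocol 8.3.1.2 asks for adverse event onset time only where it is known.
- Reconcile the compliance definitions in protocol 6.7 and SAP 4.1.1.6, and list any intended difference in SAP 3.4.

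The cost is a few sentences in the SAP and attention to onset times on two days. The downside is that an occasional profile is lost from a small group, sometimes one in which most of the drug had already been absorbed. The all-profiles summary makes that visible.
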